7.6.2 Secondary Efficacy Analysis

7.6.2.1 *Proportion of subjects who achieve resolution of steatohepatitis and no worsening of liver fibrosis at Week 24 and Week 96*

A CMH test will be used to compare the differences in proportions of subjects who achieve resolution of steatohepatitis and no worsening of liver fibrosis at Week 24 and Week 96 between the EFX arms and the placebo arm, adjusting for stratification factors. The analysis will be performed using the LBAS. The point estimates and 95% CIs for the differences in proportions, and p-values will be calculated. The 95% CI will be constructed using the Miettinen and Nurminen method. In addition, the odds ratio and risk ratio point estimate and 95% CI will be summarized for each EFX arm compared to placebo.

The same analysis will be repeated on the PPS and FAS for Week 24 and repeated on the FAS, Week 24 LBAS, and MFAS for Week 96. For any subjects with a missing efficacy value, the efficacy variable will be considered as non-responder.

A descriptive summary will present the shift from Week 24 response to Week 96 response for the Week 24 LBAS, subjects with a Week 24 biopsy but missing Week 96 biopsy will be summarized in the missing category in this summary. In addition, a descriptive summary will present the number of subjects with steatohepatitis resolution at Week 24 (with no improvement in fibrosis) and the number of subjects with fibrosis improvement (≥ 1 stage) with no worsening of steatohepatitis at Week 96.

7.6.2.2 *Proportion of subjects who achieve improvement in liver fibrosis (\geq one stage) and no worsening of steatohepatitis at Week 96*

A CMH test will be used to compare the differences in proportions of subjects who achieve improvement in liver fibrosis (\geq one stage) and no worsening of steatohepatitis at Week 96 between the EFX arms and the placebo arm, adjusting for stratification factors. The analysis will be performed using the LBAS. The point estimates and 95% CIs for the differences in proportions, and p-values will be calculated. The 95% CI will be constructed using the Miettinen and Nurminen method. In addition, the odds ratio and risk ratio point estimate and 95% CI will be summarized for each EFX arm compared to placebo.

CONFIDENTIAL

Statistical Analysis Plan

Sponsor Name: Akero Therapeutics, Inc.
Sponsor Protocol ID: AK-US-001-0102

The same analysis will be repeated on the FAS, Week 24 LBAS, and MFAS at Week 96. For any subjects with a missing efficacy value, the efficacy variable will be considered as non-responder.

A descriptive summary will present the shift from Week 24 response to Week 96 response for the Week 24 LBAS, subjects with a Week 24 biopsy but missing Week 96 biopsy will be summarized in the missing category in this summary. In addition, a descriptive summary will present the number of subjects with one stage fibrosis improvement at Week 24 with no worsening of steatohepatitis that shift to ≥ 2 stage improvement in fibrosis at Week 96.

7.6.2.3 Proportion of subjects who achieve improvement in liver fibrosis (\geq one stage) at Week 24 and Week 96

A CMH test will be used to compare the differences in proportions of subjects who achieve improvement in liver fibrosis (\geq one stage) at Week 24 and Week 96 between the EFX arms and the placebo arm, adjusting for stratification factors. The analysis will be performed using the LBAS. The point estimates and 95% CIs for the differences in proportions, and p-values will be calculated. The 95% CI will be constructed using the Miettinen and Nurminen method. In addition, the odds ratio and risk ratio point estimate and 95% CI will be summarized for each EFX arm compared to placebo.

The same analysis will be repeated on the PPS and FAS for Week 24 and repeated on the FAS, MFAS, and Week 24 LBAS for Week 96. For any subjects in the FAS with a missing efficacy value, the efficacy variable will be considered as non-responder.

A descriptive summary will present the shift from Week 24 response to Week 96 response for the Week 24 LBAS, subjects with a Week 24 biopsy but missing Week 96 biopsy will be summarized in the missing category in this summary.

7.6.2.4 Change from baseline in hepatic fat fraction measured by MRI-PDFF at Week 24 and Week 96

An analysis of covariance (ANCOVA) model with baseline covariate will be used to evaluate the changes and percent changes from baseline in hepatic fat fraction between the EFX arms and the placebo arm at Week 24, controlling for stratification factors. A mixed-model repeated-measures (MMRM) with baseline covariate will be used to evaluate the changes and percent changes from baseline in hepatic fat fraction between the EFX arms and the placebo arm at Week 24, Week 48, and Week 96, controlling for stratification factors. Least square (LS) means, 95% CIs, and p-values will be presented. The analysis will be performed using the MRI-PDFF Analysis Set.

CONFIDENTIAL

Statistical Analysis Plan

Sponsor Name: Akero Therapeutics, Inc.
Sponsor Protocol ID: AK-US-001-0102

7.6.2.5 Change from baseline of lipoproteins and markers of lipid metabolism

An MMRM model with baseline covariate will be used to evaluate the changes and percent changes from baseline in lipoproteins (Lp (a), total cholesterol, triglycerides, Non-HDL-C, HDL-C, LDL-C, and LDL-P) and markers of lipid metabolism (ApoB and ApoC-III) between the EFX arms and the placebo arm at scheduled visits, controlling for stratification factors. Least square (LS) means, 95% CIs, and p-values will be presented. The analysis will be performed using the FAS.

Non-HDL cholesterol will be calculated as Total Cholesterol - HDL-C.

Summaries and boxplots will be presented for actual values and changes from baseline in Lp (a), total cholesterol, triglycerides, Non-HDL-C, HDL-C, LDL-C, LDL-P, and ApoB and ApoC-III at the collection time points defined in the Schedule of Assessments by treatment group.

7.6.2.6 Change from baseline of glycemic control biomarkers

An MMRM model with baseline covariate will be used to evaluate the changes and percent changes from baseline in HbA1c, C-peptide, Adiponectin, and HOMA-IR between the EFX arms and the placebo arm at scheduled visits, controlling for stratification factors. LS means, 95% CIs, and p-values will be presented. The analysis will be performed using the Biomarkers Analysis Set.

Summaries and boxplots will be presented for actual values and changes from baseline in HbA1c, C-peptide, Adiponectin, and HOMA-IR at the collection time points defined in the Schedule of Assessments by treatment group.

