4.3. Exclusion Criteria

Subjects meeting any of the following criteria are not eligible for study participation:

1. Weight loss > 5% in the 3 months prior to screening until randomization or from the time of the diagnostic liver biopsy until randomization, whichever is longer.
2. Presence of cirrhosis on liver biopsy (stage 4 fibrosis).
3. Type 1 diabetes.
4. Uncontrolled Type 2 diabetes defined as:
 - a. Insulin dose adjustment >35% within 30 days prior to screening through randomization,
 - b. Symptoms of the following within 3 months prior to screening: acutely decompensated blood glucose control (e.g., thirst, polyuria, weight loss), or a history of diabetic ketoacidosis, or a history of hyperglycemic hyperosmolar state
5. Hypoglycemia unawareness, hospitalization due to hypoglycemia, or history of severe hypoglycemia (hypoglycemia requiring outside assistance to regain normal neurologic status) within 3 months prior to screening.
6. Subjects with osteoporosis, defined as a T-score of -2.5 or lower at screening.
7. Poorly controlled hypertension (systolic blood pressure > 160 mm Hg, or diastolic blood pressure > 100 mm Hg).
8. Any prior history of decompensated liver disease including ascites, hepatic encephalopathy (HE), or variceal bleeding.
9. History of pancreatitis.
Note: Subjects with a history of gallstone pancreatitis and subsequent cholecystectomy may be allowed to participate upon approval by the Medical Monitor.
10. Chronic hepatitis B virus (HBV) infection (hepatitis B surface antigen [HBsAg]) positive or acute hepatitis A infection (hepatitis A IgM antibody positive).
11. Chronic hepatitis C virus (HCV) infection (HCV antibody [Ab] and HCV ribonucleic acid [RNA] positive). Subjects cured of HCV infection < 2 years prior (based on date of RNA polymerase chain reaction [PCR] negative confirmation following conclusion of treatment) to the screening visit are not eligible.
12. Prior (< 2 years prior to screening) or planned (during the study period) bariatric surgery (e.g., gastroplasty, roux-en-Y gastric bypass). Surgery failure or reversal or removal of intragastric balloon > 2 years prior to screening would be acceptable.

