	Insulin	Must be on a stable dose(s) for at least 3 months prior to the diagnostic liver biopsy through randomization. If possible, the dose of this medication should remain stable through the end of treatment. EFX is expected to improve insulin sensitivity, subjects on insulin with variable blood glucose levels should be reminded of the symptoms of hypo- and hyper-glycemia and how to correct them.
	Metformin	Dose adjustments (but not initiation or discontinuation) for metformin are allowed in the 3 months prior to diagnostic liver biopsy. If possible, the dose of this medication should remain stable afterwards through the end of treatment.
	Sulfonylureas or other antidiabetic medication(s)	Must be on a stable dose(s) for at least 3 months prior to the diagnostic liver biopsy through randomization. If possible, the dose of this medication should remain stable through the end of treatment. EFX is expected to improve insulin sensitivity, subjects on Sulfonylureas or other antidiabetic medications with variable blood glucose levels should be reminded of the symptoms of hypo- and hyper-glycemia and how to correct them.
	Other weight loss, or lipid-modifying medication(s)	Must be on a stable dose(s) for at least 3 months prior to the diagnostic liver biopsy through randomization. If possible, the dose of this medication should remain stable through the end of treatment.

^a A stable dose is defined as no changes in prescribed dose, new medications, or discontinuation

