3.2 Secondary Efficacy Endpoints

The secondary endpoints are:

- Proportion of subjects who achieve resolution of steatohepatitis (defined as a NAS of 0-1 for inflammation, 0 for ballooning, and any value for steatosis) and no worsening of liver fibrosis as determined by the NASH CRN criteria at Week 24 and Week 96.
- Proportion of subjects who achieve improvement in liver fibrosis by \geq one stage (NASH CRN fibrosis score) and no worsening of steatohepatitis (defined as no increase in NAS for ballooning, inflammation, or steatosis) at Week 96.
- Proportion of subjects who achieve improvement in liver fibrosis by \geq one stage (NASH CRN fibrosis score) at Week 24 and Week 96.
- Change from baseline in hepatic fat fraction measured by MRI-PDFF at Week 24 and Week 96.
- Change from baseline of lipoproteins – Lp (a), total cholesterol, triglycerides, Non-HDL-C, HDL-C, LDL-C, and LDL-P and in markers of lipid metabolism (ApoB and ApoC-III).
- Change from baseline of markers of glycemic control – HbA1c, C-peptide, Adiponectin and HOMA-IR.
- Change from baseline in non-invasive markers of fibrosis – ELF, Pro-C3, C3M, NIS-4 and liver stiffness assessed by transient elastography (FibroScan[®]).
- Change from baseline of body weight.

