5.7 Biomarkers Analysis Set

The Biomarkers Analysis Set will include data from subjects in the Safety Set who have the necessary baseline and on-study measurements to provide interpretable results for the specific biomarkers or parameters of interest.

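### HOMA-IR is analysed with insulin-treated subjects included by default, so this secondary endpoint cannot be read cleanly as insulin resistance

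*SAP*

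**What the plan says.** Both documents name HOMA-IR as a secondary endpoint; SAP 3.2 lists "Change from baseline of markers of glycemic control – HbA1c, C-peptide, Adiponectin and HOMA-IR". SAP 7.6.2.6 fits an MMRM to changes and "percent changes from baseline in HbA1c, C-peptide, Adiponectin, and HOMA-IR between the EFX arms and the placebo arm", with the baseline value and the stratification factors (type 2 diabetes status and fibrosis score), and reports LS means, 95% CIs and p-values. It adds: "The analysis will be performed using the Biomarkers Analysis Set". SAP 5.7 defines that set as Safety Set subjects who "have the necessary baseline and on-study measurements to provide interpretable results for the specific biomarkers or parameters of interest".

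Insulin users are eligible. Protocol 4.3, exclusion 4a, bars only "Insulin dose adjustment >35% within 30 days prior to screening through randomization". Protocol 5.3, Table 4, lists insulin as conditionally allowed: "Must be on a stable dose(s) for at least 3 months prior to the diagnostic liver biopsy through randomization". After randomization, a stable dose is requested only where possible. The same entry notes that "EFX is expected to improve insulin sensitivity, subjects on insulin with variable blood glucose levels should be reminded" of hypo- and hyperglycemia symptoms.

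Neither document gives a HOMA-IR formula, describes the insulin assay, states how many subjects are expected to use insulin, or plans any HOMA-IR analysis by insulin use. The subgroups for glycemic markers in SAP Table 4 are baseline T2D and statin use.

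**The concern.** HOMA-IR is read as insulin resistance; protocol 1.4.1.3 uses it that way for Phase 2a. The standard index multiplies fasting insulin by fasting glucose and presumes that the insulin is the subject's own. In a subject who injects insulin, the measured value also depends on the preparation, the time since the last injection and how much of it the assay detects. The fasting requirement in protocol Table 5 controls food, not injected insulin.

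There are two consequences. A minority with high and variable values widens the confidence interval when change is analysed on its original scale. Also, because the protocol expects EFX to improve insulin sensitivity and does not fix insulin doses on study, doses may move differently by arm and take the index with them. At stake is the meaning and precision of one named secondary endpoint.

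**Working it through.** **Stated figure.** There is none to reproduce. The documents give no SD, effect size or power for HOMA-IR.

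**Are insulin users in the analysis?**
1. Eligibility: yes (exclusion 4a and Table 4 of the protocol).
2. Analysis set: membership under SAP 5.7 turns on having the needed measurements. Insulin users have them, so they are in by default.
3. Model: it adjusts for T2D status, not insulin use.
4. Medication review: the check on Table 4 dose stability (notes to SAP Table 2) serves the Per Protocol Set. SAP Table 3 assigns glycemic markers to the Biomarkers Analysis Set only.

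**Illustration 1: measured insulin falls, all else unchanged.** Assumed formula: HOMA-IR = insulin (µU/mL) × glucose (mmol/L) / 22.5. Assumed values:
- non-user: 20 × 6 / 22.5 = 5.33
- user: 60 × 8 / 22.5 = 21.33

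With 10% users the arm mean is 0.90 × 5.33 + 0.10 × 21.33 = 6.93. If users' measured insulin falls 20%, the arm mean falls by 0.10 × 21.33 × 0.20 = 0.43 (6.2%). If it falls 50%, the arm mean falls by 1.07 (15.4%).

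| Share of users | Arm mean | Fall in arm mean (20% to 50% less insulin) |
|---|---|---|
| 5% | 6.13 | 0.21 to 0.53 (3.5-8.7%) |
| 10% | 6.93 | 0.43 to 1.07 (6.2-15.4%) |
| 20% | 8.53 | 0.85 to 2.13 (10.0-25.0%) |

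**Illustration 2: chance imbalance.** With 40 per arm (protocol 5.2.2) and binomial sampling, two arms differ by 4 or more users with probability about 7%, 18% and 33% at 5%, 10% and 20% users.

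**Illustration 3: precision and power.** This simulates 3,000 trials per setting, 40 per arm, with ANCOVA of change on treatment and baseline as a simplification of the MMRM. Assumptions: median HOMA-IR 6, log-SD 0.5, baseline to follow-up correlation 0.7, true EFX reduction 40%, two-sided 5% test. Users' insulin is multiplied by a random factor between 1 and the stated maximum. Ranges cover repeat runs of the same set-up.

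| Setting | SE | Power |
|---|---|---|
| Users excluded | 0.52-0.57 | 0.998-0.999 |
| 5% users, up to 5x, new factor each visit | 0.74 | 0.98 |
| 15%, up to 5x, new factor each visit | 0.96-1.09 | 0.92-0.93 |
| 15%, up to 5x, persistent with 20% visit noise | – | 0.98 |
| 15%, up to 5x, identical at both visits | – | 0.996 |
| 20%, up to 8x, new factor each visit | 1.62-1.92 | 0.70-0.72 |
| 20%, up to 8x, persistent with 20% visit noise | – | 0.93-0.94 |
| 20%, up to 8x, identical at both visits | – | 0.98 |

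On the log scale the same contaminated data recover the 40% reduction (estimate -0.51 = ln 0.6), with power about 0.995 or higher.

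The raw estimate moves from -2.70 to between -3.28 and -3.48 at 15% users and up to 5x. This is mainly a scale effect. The uncontaminated mean is 6 × exp(0.5²/2) = 6.80, and 40% of it is 2.72. Average inflation is 1 + 0.15 × (3 - 1) = 1.30, and 2.72 × 1.30 = 3.54.

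**No true effect.** Rejection stays at about 4-5%. If measured insulin is 30% lower in EFX users only (15% users, up to 5x), the estimate is about -0.84 and rejection 9-13%.

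**The case against.** The strongest reply has five parts.

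- **SAP 5.7 already asks for interpretable results.** The phrase is parameter-specific but states no rule about insulin. If exclusion is intended, it has to be written down before unblinding.
- **A nearly clean analysis exists.** Type 1 diabetes is excluded, so baseline insulin users should sit in the T2D stratum, and the non-T2D subgroup should be nearly free of them. This stands. But it drops every diabetic subject who does not inject insulin, and the T2D subgroup still mixes users with non-users.
- **The large losses need a distortion redrawn at every visit.** This stands in good part. Draws are fasting morning samples and doses are stable before randomization, so a persistent distortion is plausible, and power is then 0.93 or higher. Much of the loss also comes from the untransformed scale.
- **A dose cut with steady glucose means better sensitivity, so a fall in HOMA-IR points the right way.** This largely stands for direction, and Illustration 1's unchanged resistance is an extreme case. The size of the fall would still track prescribing as well as resistance.
- **Phase 2a gives no sign of trouble.** Protocol 1.4.1.3 reports HOMA-IR reductions of 7.675 and 8.775 at 50 and 70 mg. A reader might infer that insulin users or outliers drove them, but the text says nothing about either.

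**Conclusion.** The concern holds as an interpretability and precision problem for one secondary endpoint. Insulin users are in the HOMA-IR analysis by default, and nothing separates them out. In illustrations with 5-20% users, the SE rises from about 0.5 to 0.7-1.9 and power falls from above 0.99 to 0.70-0.98; if the distortion is identical at both visits, power is hardly affected. The share of users, the inflation and its stability are all assumptions.

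A reader might go further and infer that in these subjects the index measures injected insulin and not resistance, or that the comparison is invalid. The documents do not support that. They describe no assay, and subjects with type 2 diabetes may still secrete insulin, so the two sources are mixed. False positives do not rise unless insulin doses fall by arm, which the documents make possible but do not show. The primary endpoint is untouched. This is a cheap improvement, not a flaw that threatens the trial.

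**What to change.** In SAP 7.6.2.6:

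1. Add the HOMA-IR MMRM in subjects not using insulin at baseline, flagged from the concomitant-medication eCRF, and name it as the analysis used to interpret insulin resistance. The restriction uses baseline information only, so it does not select on post-randomization events.
2. Report the all-subject analysis beside it, preferably also on the log scale.
3. Do not set values to missing after on-study insulin start in the main version. Starting insulin may reflect worsening control and differ by arm. Show that version only as a sensitivity analysis.
4. Do not offer C-peptide as the substitute for insulin users, since injected insulin can affect it too.

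If Week 24 results are already unblinded when this is added, label the restricted analysis supplementary for those visits. The cost is a sentence or two in the SAP, one flag, and a smaller n for this endpoint: at 5-20% users, 2 to 8 of 40 per arm (0.05 × 40 = 2; 0.20 × 40 = 8). No dose or eligibility rule changes.

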7.6.2.7 Change from baseline of serum fibrosis biomarkers

An MMRM model with baseline covariate will be used to evaluate the changes and percent changes from baseline in ELF, Pro-C3, C3M, and NIS-4 between the EFX arms and the placebo arm at scheduled visits, controlling for stratification factors. LS means, 95% CIs, and p-values will be presented. The analysis will be performed using the Biomarkers Analysis Set and LBAS.

Summaries and boxplots will be presented for actual values and changes from baseline in ELF, Pro-C3, C3M, and NIS-4 at the collection time points defined in the Schedule of Assessments by treatment group.

7.6.2.8 Change from baseline in liver stiffness and controlled attenuation parameter (CAP) as evaluated by FibroScan

An ANCOVA model with baseline covariate will be used to evaluate the changes and percent changes from baseline in liver stiffness (kPa) and CAP (dB/m) between the EFX arms and the placebo arm at Week 24, controlling for stratification factors. An

CONFIDENTIAL

Statistical Analysis Plan

Sponsor Name: Akero Therapeutics, Inc.
Sponsor Protocol ID: AK-US-001-0102

MMRM model with baseline covariate will be used to evaluate the changes and percent changes from baseline in liver stiffness and CAP between the EFX arms and the placebo arm at Weeks 24, 48, and 96, controlling for stratification factors. LS means, 95% CIs, and p-values will be presented. The analysis will be performed using the FAS and LBAS.

Summaries and boxplots will be presented for actual values and changes from baseline in liver stiffness at the collection time points defined in the Schedule of Assessments by treatment group.

In addition, the proportion of patients with interquartile range (IQR)/Median ratio <30% for liver stiffness and IQR <40dB/m for CAP, will be summarized by visit.

7.6.2.9 *Change from baseline of body weight*

An MMRM model with baseline covariate will be used to evaluate the changes and percent changes from baseline in body weight between the EFX arms and the placebo arm at scheduled visits, controlling for stratification factors. LS means, 95% CIs, and p-values will be presented. The analysis will be performed using the FAS.

Summaries and boxplots will be presented for actual values and changes from baseline in body weight at the collection time points defined in the Schedule of Assessments by treatment group.

7.6.3 Exploratory Analysis

The same efficacy analyses used for the secondary efficacy variables will be used for the exploratory efficacy variables.

7.6.3.1 *Proportion of subjects who achieve resolution of steatohepatitis AND improvement in liver fibrosis (\geq one stage) at Week 24 and Week 96*

A CMH test will be used to compare the differences in proportions of subjects who achieve resolution of steatohepatitis AND improvement in liver fibrosis (\geq one stage) at Week 24 and Week 96 between the EFX arms and the placebo arm, adjusting for stratification factors. The analysis will be performed using the LBAS. The point estimates and 95% CIs for the differences in proportions, and p-values will be calculated. The 95% CI will be constructed using the Miettinen and Nurminen method. In addition, the odds ratio and risk ratio point estimate and 95% CI will be summarized for each EFX arm compared to placebo.

The same analysis will be repeated on the PPS for Week 24. The analysis will be repeated using the MFAS, Week 24 LBAS, and Week 96 LBAS at Week 96.

CONFIDENTIAL

Document Date: 07 Feb 2024

Page 36 of 60
ST-AD-008 version 05

Statistical Analysis Plan

Sponsor Name: Akero Therapeutics, Inc.
Sponsor Protocol ID: AK-US-001-0102

A descriptive summary will present the shift from Week 24 response to Week 96 response for the Week 24 LBAS, subjects with a Week 24 biopsy but missing Week 96 biopsy will be summarized in the missing category in this summary.

